# 9.7 Extent of Exposure and Treatment Compliance

The extent of exposure is defined as the number of days between the first ring insertion until removal and will be summarized by cycle and treatment group. The total extent of exposure (across all cycles) will be summarized by treatment group and overall. This will be done both including and excluding known periods of intermittent removals of the vaginal ring if applicable.

The number of days of rescue analgesics use and the percentage of days on rescue analgesics will be similarly summarized.

## 9.8 Safety Endpoints

### **General Considerations**

This section describes the descriptive analyses of safety endpoints and routine safety assessments. The safety endpoints, highlighted in grey in Table 9-2, will be analyzed for the safety analysis set.

#### **Changes in Bone-turnover Markers**

Changes in bone-turnover markers will be analyzed by an ANCOVA model, estimating adjusted treatment contrasts at cycle 4, as described in Table 9-2 in section 9.6.3.

#### ECG and Echocardiography

Changes in ECG parameters, including PR interval, QT interval, QTcF interval and QRS interval at cycle 4 will be summarized by cycle and treatment group and in total.

The proportion of subjects with clinically significant echocardiography findings will be tabulated by cycle and treatment group and in total.

#### **Questionnaire for Impulsive-Compulsive Disorders**

Frequency-tables for each item of the questionnaire for impulsive-compulsive disorders as well as the proportion of subjects having potential behaviors associated with impulse control disorders will be presented by cycle, treatment and in total.

### Adverse Events

Treatment-emergent adverse eventsg will be summarized overall and tabulated by SOC and preferred term using MedDRA. The version of MedDRA will be documented. The total number of subjects reporting an adverse event, the percentage of subjects (%) with an adverse event, and the number of events reported will be presented.

Summary tables will be prepared for the following: all adverse events, adverse events by causality (reasonable possibility / no reasonable possibility), adverse events leading to death, adverse events by intensity (mild / moderate/ severe), adverse reactions by intensity (mild / moderate/ severe), SAEs, adverse events leading to discontinuation, adverse events with an incidence of at least 5% in any treatment group, non-SAEs with an incidence of at least 5% in any treatment group. A separate data listing will be provided for pre-treatment adverse events.h Listings of adverse events will also indicate whether or not the adverse event occurs during the COVID-19 trial hold.

#### Safety Laboratory Variables

Safety laboratory variables will be grouped under "hematology" and "clinical chemistry".

The baseline is taken on LH+7 of cycle -1. Post-baseline clinical laboratory values are taken on LH+7 of cycle 4.

The circulating levels of clinical chemistry and hematology parameters including changes from baseline will be tabulated for each time point for each laboratory variable.

Shift tables will be prepared to compare baseline values to the values at the respective post-baseline visits, using a categorization of low, normal and high values defined according to the reference ranges provided by the central laboratory.

For each laboratory variable, a summary table will be prepared displaying the proportion of subjects who have at least one post baseline markedly abnormal value. The denominator will be the number of subjects with baseline and at least one post baseline value. The table will also include a break-down by classification of the baseline value. Markedly abnormal criteria for the safety laboratory values will be specified in the SAP.

All laboratory values will be listed by subject number and time point. Values outside the reference range and markedly abnormal values will be flagged.

#### Urinalysis

Urinalysis parameters will be summarized descriptively.

<sup>g A treatment-emergent adverse event is any adverse event occurring after start of IMP and before the end-of-trial visit, or a pre-treatment adverse event or pre-existing medical condition that worsens in intensity after start of IMP and before the end-of-trial visit.

<sup>h A pre-treatment adverse event is any adverse event occurring after signed informed consent and before start of IMP or a pre-existing condition that worsens in intensity after signed informed consent but before start of IMP.

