#### 6.1.1 **Premature Discontinuation**

In case of premature discontinuation, an end-of-treatment visit (see section 6.4.6) should be arranged as soon as possible (preferably within 7 days of the last ring removal). Subjects who are prematurely discontinued from the treatment due to adverse events will be asked to attend an end-of-trial visit (see section 6.5.1) within 2 weeks of the end-of-treatment visit. If subjects are discontinued for other reasons, the end-of-treatment and end-of-trial visits can coincide.

If a discontinued subject is found with an ongoing adverse event classified as serious or considered to have a reasonable possible causality to the IMP at their last trial visit, the site staff should follow up until the event is resolved (see section 8.6).

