## 7.2.2.11 Adverse Events

Adverse events will be recorded from the signing of informed consent(s) for participation in the trial until the end-of-trial visit. For each adverse event, the following parameters will be recorded by the investigator on the Adverse Event Log: description of event, date and time of onset, intensity, causal relation to IMP, action taken to IMP, other actions taken, seriousness of the adverse event, date and time of outcome, and outcome. A search for predefined preferred terms and reported terms will be conducted on all treatment-emergent adverse events to identify those potentially related to behaviors associated with impulse control disorders. See section 8.

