#### 8 ADVERSE EVENTS

#### 8.1 Adverse Event Definition

An adverse event is any untoward medical occurrence in a subject participating in a clinical trial. It includes:

- Any unfavorable and unintended sign, symptom or disease temporally associated with the use of the IMP, whether or not considered to be caused by the IMP.
- Adverse events commonly observed and adverse events anticipated based on the pharmacological effect of the IMP.
- Any laboratory abnormality, vital signs, ECG, echocardiography or finding from physical or gynecological examination including transvaginal ultrasound assessed as clinically significant by the investigator [*note*: findings from assessments and examinations done during the screening period are not adverse events, but are recorded as medical history.]
- Accidental injuries, reasons for any medical, nursing or pharmacy consultation, or reasons for admission to hospital or surgical procedures.

All adverse events will be coded by Ferring Pharmacovigilance using MedDRA (the MedDRA version will be documented).

Medication errors of IMP will be captured by ring acceptability questionnaire and/or a medication error form in the e-CRF.

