#### Date and Time of Onset

The date of onset is the date when the first sign(s) or symptom(s) were first noted. If the adverse event is an abnormal clinically significant laboratory test or outcome of an examination, the onset

<sup>f Exception: if an adverse event with onset before the first IMP administration (i.e. a pre-treatment adverse event) changes in intensity after the IMP administration, this must be recorded as two separate events. The initial adverse event should be recorded with outcome "not recovered" and the date and time of outcome is when the intensity changed. The second adverse event should be recorded with date and time of onset when the intensity changed.

date is the date the sample was taken or the examination was performed.

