10.2 Adverse Events

AEs are classified according to MedDRA version 20.0.

Written narratives will be issued for all serious AEs (including deaths) and AEs leading to withdrawal.

A pre-treatment adverse event is any adverse event occurring after signed informed consent and before start of IMP or a pre-existing condition that worsens in intensity after signed informed consent but before start of IMP. Pre-treatment AEs will be presented in a separate data listing only.

A treatment-emergent adverse event (TEAE) is any adverse event occurring after start of IMP and before the end-of-trial visit, or a pre-treatment adverse event or pre-existing medical condition that worsens in intensity after start of IMP and before the end-of-trial visit.

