10.3.2 Laboratory Variable Changes Relative to Normal Range

As the trial has been prematurely discontinued, it has been decided, due to the low number of subjects, that no shift tables will be prepared. Clinical significant changes in laboratory values are presented in the AE tables.

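### The treatment-emergent window closes before the end-of-trial visit, so findings dated on that visit day drop out of the TEAE tables, and SAP 10.1 sets a conflicting window

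*Protocol*

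**What the plan says.** **Definition.** Footnote g to Protocol 9.8 reads: "A treatment-emergent adverse event is any adverse event occurring after start of IMP and before the end-of-trial visit". SAP 10.2 repeats it: "A treatment-emergent adverse event (TEAE) is any adverse event occurring after start of IMP and before the end-of-trial visit". In both documents the second half of the definition, on conditions that worsen, has the same upper limit. Pre-treatment events are those before the first ring.

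**Onset dates.** Protocol 8.2.2 has two rules. For symptoms: "The date of onset is the date when the first sign(s) or symptom(s) were first noted". For a clinically significant laboratory result or examination outcome, the onset "date is the date the sample was taken or the examination was performed". Protocol 8.1 lists what can become an adverse event: "Any laboratory abnormality, vital signs, ECG, echocardiography or finding from physical or gynecological examination including transvaginal ultrasound assessed as clinically significant by the investigator".

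**Collection.** Protocol 7.2.2.11: "Adverse events will be recorded from the signing of informed consent(s) for participation in the trial until the end-of-trial visit". Section 6.5.1 makes adverse-event recording one of the procedures of that visit, alongside a chemistry and hematology sample.

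**Early stopping.** Protocol 6.1.1 brings women who stop because of an adverse event back for a separate end-of-trial visit within two weeks. For the rest: "If subjects are discontinued for other reasons, the end-of-treatment and end-of-trial visits can coincide". Section 6.4.6 then asks for both sets of assessments at the last visit.

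**SAP tables.** SAP 10.1 sets its own windows by onset date. Part A runs to the end-of-cycle 4 visit inclusive, or to the date of premature discontinuation if that visit is missing. Part B runs from the day after the end-of-cycle 4 visit to last ring removal inclusive. SAP 10.3.2 drops the laboratory shift tables and adds: "Clinical significant changes in laboratory values are presented in the AE tables".

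**The concern.** An event can be collected, dated and judged clinically significant, and still belong to no reporting class. The summary tables in SAP 10.2.1 and 10.2.2 are all built on TEAEs, so such an event is counted in none of them.

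Whether a finding counts can also turn on why the woman stopped. Suppose two women show the same blood-pressure drop on standing at their end-of-treatment assessment; Protocol 7.4.15 makes that drop an adverse event. If one stopped because of an adverse event and returns later, her finding meets the definition. If the other stopped for another reason and had a combined visit, hers does not. Reason for stopping arises after randomization, so it should not decide which safety findings are tabulated.

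The laboratory point has extra weight because the SAP gives the AE tables as a reason for not producing shift tables. For end-of-trial samples the definition keeps those changes out of the AE tables.

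**Working it through.** The plan gives no figure for TEAE counts, so the check is one of date logic, plus a bound on the number of women.

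**1. Is *before* meant strictly?** SAP 10.1 states explicitly that the limit date is included when it wants an inclusive limit. SAP 10.2, one section later, does not. A programmer following the text would code onset < end-of-trial date.

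**2. Test cases.** Day numbers are illustrative and count from first insertion. Completer: visit 10 on day 120, visit 11 on day 150. Early stopper: discontinuation on day 60.

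| Case | Onset | End-of-trial visit | As written (onset < visit) | Inclusive (onset ≤ visit) | Inside SAP 10.1 Part A |
|---|---|---|---|---|---|
| 1. Completer, symptom begun earlier, reported at visit 11 | 145 | 150 | yes | yes | no |
| 2. Completer, visit 11 laboratory finding | 150 | 150 | no | yes | no |
| 3. Completer, visit 10 examination or laboratory finding | 120 | 150 | yes | yes | yes |
| 4. Non-AE stop, combined visit on the discontinuation day | 60 | 60 | no | yes | yes |
| 5. Non-AE stop, combined visit 5 days later | 65 | 65 | no | yes | no |
| 6. AE stop, end-of-treatment examination finding | 65 | 79 | yes | yes | no |
| 7. AE stop, end-of-trial laboratory finding | 79 | 79 | no | yes | no |

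**3. What the table shows.**
- Cases 2, 4, 5 and 7 fail the definition only because onset falls on the end-of-trial visit day. The inclusive wording admits all seven.
- Cases 5 and 6 are the same finding on the same day. Only the woman who stopped for an adverse event has a TEAE.
- Case 4 is inside Part A under SAP 10.1 but not a TEAE under SAP 10.2. No sentence says which rule governs.
- Cases 1 and 6 are TEAEs outside Part A. For a four-cycle completer the last ring comes out at visit 10, so the Part B window is empty and the whole follow-up cycle belongs to neither table. Rewording the definition alone would not bring case 2 into a SAP table.

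**4. Which findings.** For completers, visit 11 schedules chemistry, hematology and a pregnancy test. Vital signs, ECG, echocardiography, physical and gynecological examination and ultrasound belong to visit 10. At a combined visit, vital-sign, physical, gynecological, ultrasound and laboratory findings carry the excluded date, as do ECG and echocardiography if done that day. This treats vital signs and ECG as examinations under 8.2.2, which is how I read 8.1.

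**5. How many women.** Plan's figures (Protocol 9.1): 52 / (1 − 0.25) = 69.3, rounded up to 70 per group; 4 × 70 = 280 randomized; 4 × 52 = 208 evaluable. Planned drop-outs: 280 − 208 = 72. Neither document splits these by reason, and a combined visit is optional. The number with a combined last visit is therefore between 0 and 72. This counts women, not findings lost.

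**The case against.** The best reply is that little disappears. The listing in SAP 10.2.2 covers all adverse events, narratives cover serious events and withdrawals due to adverse events, SAP 10.3.1 summarizes laboratory values at each time point, and SAP 10.3.3 lists women with abnormal values. SAP 11 and 12 say change from baseline can be read from the listings. That stands: the gap is in the TEAE tables, not in reporting as a whole.

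It is also fair that combined visits are permitted and not required, that SAP 10.1 can admit a combined-visit finding dated on the discontinuation day, and that Protocol 1.3 reports no clinically significant laboratory, vital-sign, ECG or examination effects in phase 1, so affected events may be few. The first two points make the outcome uncertain; they do not make the rule sound.

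A reader might go further than the documents allow in four ways:
- *Everything found at the end-of-trial visit is lost.* No. Symptoms first noted earlier keep their earlier onset. Behaviors picked up by the impulse-control questionnaire concern past periods (Protocol 7.2.2.10) and are more naturally dated before the visit.
- *Half of the post-baseline safety samples cannot yield a TEAE.* One of two holds only under protocol version 6. SAP 10.3 plans three post-baseline measurements, and most women were randomized under version 5.0.
- *The arm comparison is biased in a known direction.* Neither document gives reasons for stopping by arm, so no direction can be claimed.
- *These are all on-treatment findings.* A completer's visit 11 sample comes about a cycle after the last ring was removed.

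**Conclusion.** The point holds as a boundary error in a stated rule, present in both documents, together with a conflict between SAP 10.1 and SAP 10.2. Taken literally, findings with onset on the end-of-trial visit day fall outside the TEAE tables. The exposure is end-of-trial laboratory findings and same-day events for anyone attending that visit, plus the end-of-treatment findings of women with a combined last visit: 0 to 72 women at the planned size. The actual number is smaller, since the SAP records early termination with few women recruited, and it reports descriptive statistics only. The conclusion rests on reading *before* as strict, which the inclusive wording elsewhere in the SAP supports. How many findings would be affected cannot be derived from the documents. The consequence is modest, but the rule should be corrected because it is easy to do and the SAP relies on the AE tables to show laboratory changes.

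**What to change.** 1. In footnote g and in SAP 10.2, change *before* to *up to and including* ahead of the end-of-trial visit, at both occurrences in each. This matches the collection period.
2. Add one sentence: findings from samples or examinations taken at that visit count, whenever the result is returned.
3. Align SAP 10.1 with the definition. State where events found at a combined last visit go, including one held after the discontinuation date, and assign events from last ring removal through the end-of-trial visit to a named table, for example a follow-up table. Without this step a completer's end-of-trial findings still enter no SAP table.

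The cost is a few words in each document, a revised window table in SAP 10.1, one comparison operator and one added period in the programs. No new data are needed.

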### **Ring Acceptability Parameters**

Frequency-tables for each item (as applicable) of the ring acceptability questionnaire will be presented by cycle, treatment group and in total.

## Other Safety Variables

#### Vital Signs

Vital signs and the changes in vital signs will be analyzed similarly to routine safety laboratory variables. Reference ranges for vital signs will be specified in the SAP.

#### Physical and Gynecological Examination

Physical and gynecological examination findings at end-of-treatment compared to screening will be summarized in shift tables and all subjects with any abnormal finding will be listed by subject and time point. The list will include both screening and end-of-treatment assessment for comparison.

#### Transvaginal Ultrasound

Endometrial thickness, number and size of fibroids if presented and number and size of ovarian cyst if presented will be tabulated by screening, RM+7 visits of cycle 4.

#### 9.9 Interim Analysis

An interim analysis with the option to stop the trial early due to futility will be performed by an external statistician, when approximately half of the planned evaluable subjects (104 subjects) have completed the treatment period of the trial for the assessment of the primary endpoint, using unblinded data presented by treatment group.

The futility bound is set at a conditional power using current trend equal to 5%, which means that the trial could potentially be stopped for futility, if the probability of achieving a significant result in the highest remaining dose group is lower than 5% based on the observed data at the interim analysis. In case of high drop-out rate or discontinuations in the highest dose group, the analysis will be performed on the remaining dose(s). If the probability is between 5% and 90%, the sample size will be re-estimated by the external statistician based on the unblinded data available at the interim analysis and may be increased to a total of 360 subjects.

No interim analysis intended to stop the trial early due to overwhelming efficacy is planned.

#### 10 DATA HANDLING

#### **10.1** Source Data and Source Documents

#### **Source Data – ICH Definition**

Source data are defined as all information in original records and certified copies of original records of clinical findings, observations, or other activities in a clinical trial necessary for the reconstruction and evaluation of the trial. Source data are contained in source documents (original records or certified copies).

#### **Source Documents – ICH Definition**

Source documents are defined as original documents, data, and records (e.g. hospital records, clinical and office charts, laboratory notes, memoranda, subjects' diaries or evaluation checklists, pharmacy dispensing records, recorded data from automated instruments, copies or transcriptions certified after verification as being accurate copies, microfiches, photographic negatives, microfilm or magnetic media, x-rays, subject files, and records kept at the pharmacy, at the laboratories and at medico-technical departments involved in the clinical trial).

#### **Trial-specific Source Data Requirements – Ferring**

Source documents need to be preserved for the maximum period of time permitted by local requirements. For each subject screened, the investigator will indicate as a minimum in the source documents that informed consent is obtained, whether wash-out is needed, the date and the reason for wash-out if applicable and the reason for screening failure if applicable. For each subject randomized, the investigator will indicate in the source documents that the subject participates in this trial, and will record at least the following information, if applicable:

- Existence of subject (initials, date of birth)
- Confirmation of participation in trial (trial ID, subject ID)
- Informed consent(s) (date of obtaining written informed consent(s))
- Eligibility for participation in the trial (documenting all inclusion / exclusion criteria)
- Relevant medical history and menstrual history
- Visit dates
- Dates of insertion/removal of the ring
- Dispensing of IMP and ibuprofen
- Dates and doses of concomitant medications
- Adverse events (description as well as start/stop date and time)
- Reason for discontinuation
- Event of unblinding, including the reason for unblinding

The source data for analytical parameters of blood samples will be available at the central laboratory.

In addition, each subject will use an e-Diary on a daily basis to record the following specific protocol data, for which the e-PRO service provider database is considered source data:

- Assessment of endometriosis-related pain on NRS scale
- Vaginal bleeding
- Occurrence of sexual intercourse and assessment of dyspareunia (if applicable)
- Pain impact (also applicable to the weekly pain impact questions)
- Analgesic use

Note that part of the analgesic use information, such as prescriptions of hydrocodoneacetaminophen or information of other analgesics, will be recorded in the e-CRF.

At a few selected visits, subjects, study coordinators and investigators will access electronic tablets separately to record the following data, for which the e-PRO service provider database is considered source data:

- B&B scores
- EHP-30 scores
- PGIS and PGIC scores
- QICD scores
- Ring acceptability

For the eC-SSRS, the e-PRO service database is also considered source data. The text files of transcripts will be considered source documents for patient interviews.

